10.1.2 Secondary Hypotheses

It is also hypothesized that the BUP-XR, relative to the BUP-SL, group will have better:

1. Mother outcomes during pregnancy including significantly:
 - greater proportion of BUP adherent days during pregnancy
 - greater proportion of drug-negative urine samples
 - less opioid craving as assessed by the opioid craving scale
 - better prenatal care utilization as assessed with the APNCU index
2. Mother outcomes postpartum including significantly:
 - greater proportion of BUP adherent days
 - greater proportion of drug-negative urine samples
 - fewer opioid overdoses
 - less opioid craving as assessed by the opioid craving scale
3. Infant outcomes including significantly:
 - lower proportion of infants requiring opioid medication
 - shorter infant hospital length of stay
 - lower proportion of infants for whom adjunct medications are used to treat NOWS
 - lower proportion of infants with an ICD-10 code indicative of NOWS
 - larger head circumference
 - greater weight and length
 - greater gestational age at delivery
 - greater proportion of infants scoring above the ASQ-3 cut-off

10.2 Intent-to-Treat Participant Population

The intent-to-treat population is defined as the participants who are randomized to treatment for maternal outcomes, and their offspring for the infant outcomes.

10.3 Analysis Plan

Each primary and secondary efficacy outcome measure will be analyzed for the intent-to-treat (ITT) population.

The primary outcome will be assessed at a 2.5% significance level for non-inferiority, as recommended by the FDA.¹⁷⁶ If the test of BUP-XR being non-inferior to BUP-SL is statistically significant, then the superiority of the extended-release formulation over the sublingual formulation will be evaluated. There is no need to adjust for this second test if the initial test of non-inferiority is statistically significant. The infant key secondary outcome will be analyzed at the 5% significance level for superiority, and will be interpreted cautiously given the lack of adjustment for multiple testing and will use confidence intervals where possible. The other key secondary outcome (illicit opioid abstinence during postpartum) will be assessed at a 2.5% significance level for non-inferiority.

10.3.1 Non-Inferiority Margin

As noted in **section 4.0**, there is a dearth of research on the treatment of OUD in pregnant women and, thus, no data upon which to base the non-inferiority margin for CTN-0080 is available. However, the OPTIMA study, a current non-inferiority trial comparing BUP/NX-SL to methadone in non-pregnant participants, is utilizing a primary outcome similar to the CTN-0080 primary outcome (i.e., proportion of opioid-free UDSs collected at the time of the weekly medication check with missing UDSs imputed as positive).¹⁷⁷ The non-inferiority margin for the OPTIMA trial is 15%, which was selected based on a literature review and expert input.¹⁷⁷ Given the more vulnerable nature of the CTN-0080 patient population in which illicit opioid use impacts the health of not only the mother but also the infant, we originally selected the more conservative margin of 11% (i.e., $\Delta = 0.11$). However, research continues to suggest that OUD in pregnant and postpartum women is a critical issue in rural communities where access to MOUD is limited.¹⁷⁸ The most cited reason for not prescribing buprenorphine by both rural physicians¹⁷⁹ and nurse practitioners/ physician assistants¹⁸⁰ with a buprenorphine waiver is concern about diversion/misuse. Since this concern would be eliminated by BUP-XR and, hence, BUP-XR has the potential to substantially increase MOUD access for pregnant/postpartum women, it was determined that the 11% margin was overly conservative. Hence, the margin was changed to 15% (i.e., $\Delta = 0.15$), which takes into account both the greater vulnerability of pregnant women with OUD and the potential of BUP-XR to substantially increase MOUD access, neither of which is present in the OPTIMA trial and which balance out to utilizing the 15% OPTIMA non-inferiority margin. As outlined in section 10.4 (Sample Size Analysis), the change in margin decreased the number of participants needed for an adequately-powered primary outcome to 176. As noted in **section 6.2**, the target sample size is approximately 200 participants, which would provide more power for secondary analyses, but the primary analysis will be adequately powered with 176 participants. This decrease in required sample size increases the feasibility of the MOMs trial, which was initiated at the start of the COVID-19 epidemic, which, in turn, adversely impacted the randomization rate at all of the study sites. Note that this non-inferiority margin will be used for both the primary outcome, as well as the key secondary outcome of postpartum illicit opioid abstinence.

10.3.2 Key Outcomes

Illicit opioid abstinence during pregnancy. As noted previously, this primary outcome measure is based on urine testing. It is operationalized as the percent of expected UDSs that are negative for illicit opioids. One UDS is expected at the time of each weekly Medication Check Visit between randomization and delivery – any missing UDS is imputed as positive (see **section 10.3.5**). The number of expected UDSs will be dependent on the length of time between randomization and

delivery, thus we operationalize this primary outcome measure as the *percent* of expected UDSs that are illicit opioid-negative.

The non-inferiority design results in the following hypotheses where μ_A is the mean in arm A and Δ the non-inferiority margin:

$$H_0(BUP - XR \text{ is inferior to BUP - SL}): \mu_{XR} - \mu_{SL} \leq -\Delta$$

$$H_1(BUP - XR \text{ is non - inferior to BUP - SL}): \mu_{XR} - \mu_{SL} > -\Delta .$$

To evaluate non-inferiority at the 2.5% significance level, the two-sided 95% confidence interval for the treatment effect, $\mu_{XR} - \mu_{SL}$, will be calculated using a mixed effects model where treatment arm is a fixed effect and the three randomization factors (site, EGA and BUP-SL status at randomization) are random effects. If the lower limit of the confidence interval is greater than -0.15 (i.e., $\Delta=0.15$), we will reject the null hypothesis and conclude non-inferiority of BUP-XR to BUP-SL. Only if the null hypothesis is rejected will superiority of BUP-XR to BUP-SL be considered. This will involve examining the two-sided 95% confidence interval for the treatment effect, $\mu_{XR} - \mu_{SL}$. If the lower limit is above zero, then we can conclude that the extended-release formulation is superior to the sublingual formulation. If this order of testing is followed, then there is no need to adjust for multiplicity.^{176, 181} Additional covariates for secondary modeling are described in **section 7.4**. In the event that the distributional assumptions involved in the mixed effects model are not met, which is likely, alternative non-parametric methods will be considered for this modelling such as quantile regression.

Total days of opioid treatment. Total days of infant opioid treatment will be obtained from the medical record. There are extensive covariates to be included in modelling for the infant outcomes (**Table 2**) at the mother-, infant-, and delivery-hospital-level. Explanation for these covariates is provided in **section 7.4**. Since this outcome measure is a count variable and there are covariates requiring adjustment, modelling will utilize Poisson regression. The treatment effect will be measured by the regression coefficient for treatment assignment in the model ($H_0: \beta=0$; $H_1: \beta \neq 0$).

Illicit opioid abstinence during postpartum. The analytic approach will follow the one outlined above for testing the primary outcome.

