7.4.1 Covariates for Mother Outcomes

Two covariates will be controlled for in the mother outcomes in addition to study site: 1) the use of other substances at baseline, which can impact both treatment adherence and illicit opioid use and 2) route of illicit opioid use (intravenous vs. not intravenous); the Phase 3 CAM2038 trial found that illicit use outcomes were significantly better for CAM2038, relative to BUP-SL, for participants with intravenous use.⁵⁹

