7.6.2 Sample Characteristics

Pregnancy-history characteristics: Pregnancy history (e.g., gravidity, parity, etc.) will be assessed by self-report and medical record data, as available, with medical record data being the preferred data source.

HIV/Hepatitis C status: HIV and Hepatitis C status will be assessed by self-report and medical record data, as available, with medical record data being the preferred data source.

Trauma history: Exposure to traumatic events is elevated in women with SUDs and is associated with worse treatment outcomes.¹⁵⁵ The Trauma History Screen is a brief, self-administered instrument with good reliability and validity.^{156, 157} The Trauma History Screen will be used to assess the participant's exposure to 14 traumatic events and the severity and duration of the emotional response to any event experienced.

Psychosocial status: The Trauma History Screen does not assess intimate partner violence, which is fairly prevalent in women with OUD, and, thus, will be supplemented with two items that have been used to assess intimate partner violence in past research.¹⁵⁸ In addition, other characteristics of interest, including living arrangements, pregnancy intention, and number of children and their custody will be assessed.

Maternal depression: The Patient Health Questionnaire-9, will be used to assess for symptoms of major depression.¹⁵⁹ It will be completed following the schedule in **Table 3**. A qualified mental health professional must assess participants reporting current suicidal intent as specified in the site clinical SOP.

Fagerström Test for Nicotine Dependence: Approximately 90% of pregnant women receiving opioid maintenance treatment smoke cigarettes,¹⁶⁰ which is associated with worse pregnancy outcomes and NAS/NOWS.^{121, 122} The Fagerström is a brief self-administered assessment of cigarette use patterns,¹⁶¹ which yields a single overall dependence score.

The Timeline Followback (TLFB) procedure:^{162, 163} will assess the participants' self-reported use of substances for the 30 days before study consent.

Thoughts about Abstinence: The Thoughts about Abstinence assessment,¹⁶⁴ which assesses desire to quit, expected success in quitting and estimated difficulty in avoiding relapse, has been found to be predictive of treatment response in pregnant substance users.¹⁶⁵ It will be completed for alcohol, drugs, and cigarettes following the schedule outlined in **Table 3**.

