8.4 Randomization Plan

Eligible participants will be randomized in a 1:1 ratio to BUP-XR or BUP-SL. The randomization process will be performed by computer by the Data and Statistics Center (DSC). A permuted block randomization procedure with random block sizes will be implemented to balance on site, whether participants are on BUP-SL at the time of randomization (yes vs. no), and EGA at time of randomization (6 weeks - 18 weeks vs. 19 weeks - 30 weeks); EGA was used as a stratification variable in the MOTHER trial.⁴³

Table 3: Overview of Assessments and Procedures																			
Perinatal Phase:	Pregnancy					Delivery & Immediate Post-partum	Post-partum												As Needed
	Pre- Screen	Screen/ Base ¹	Random- ization ²	Week 3	Monthly Post-rand ³		Month 1	Month 2	Month 3	Month 4	Month 5	Month 6	Month 7	Month 8	Month 9	Month 10	Month 11	Month 12	
Research Visits		X	X	X	X		X		X			X			X			X*	
Screening Assessments																			
Pre-screen verbal consent	X																		
Pre-screen interview	X																		
Informed Consent		X																	
Medical record releases		X																	X
Demographics/PhenX Tier 1		X																	
DSM-5 checklist		X																	
PRISM-Suicide/Homicide		X																	
Blood Chemistry ^{4,5}		X																	
Urine Pregnancy Test		X																	
Estimated Gestational Age ^{4,5}		X																	
Treatment and Research Status		X																	
Medical and Psych History (Hx)		X																	
Drop-out Risk Assessment		X																	
Weekly Medication Check Visits ⁶																			
BUP-XR administration/documentation			Weekly administration ⁶				Weekly or Monthly administration ⁷												
BUP-SL dispense/document; adherence			Weekly - Monthly dispensing ⁸				Weekly - Monthly dispensing ⁸												
Adverse Events/Serious Adverse Events			Weekly ⁶				Weekly ⁶												
Injection Site Reaction Reporting Form																			X
Urine drug screen		X	Weekly ⁶				Weekly ⁶												
Infant sedation assessment							Weekly ⁶												
Pregnancy Test (BUP-XR)							Monthly for participants on monthly BUP-XR formulation												X
Medication Check Visit Compensation			\$20 per visit not corresponding to a research visit																
Table 3 continued on next page																			

Table 3 continued on next page

Table 3: Overview of Assessments and Procedures																			
Perinatal Phase:	Pregnancy					Delivery & Immediate Post-partum	Post-partum												As Needed

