	Pre- Screen	Screen/ Base ¹	Random- ization ²	Week 3	Monthly Post-rand ³		Month 1	Month 2	Month 3	Month 4	Month 5	Month 6	Month 7	Month 8	Month 9	Month 10	Month 11	Month 12	
Research Visits		X	X	X	X		X		X			X			X			X*	
Sample Characteristics																			
Pregnancy Hx, HIV, Hepatitis C		X																	
Trauma History Screen		X																	
Psychosocial status		X																	
Pt. Health Questionnaire-9		X					X											X	
Thoughts about Abstinence		X																	
Timeline Followback (drug/alcohol/tobacco)		X																	
Fagerström		X																	
Opioid Overdose Risk Survey		X																	
Marijuana Use Assessment		X																	
Safety Assessments																			
Hospital Anxiety and Depression Scale		X		X	X		X		X			X			X			X	
Prior/Concomitant Meds		X		X	X		X		X			X			X			X	
Fetal Outcomes ⁴						X													
Maternal Delivery Outcomes ⁴						X													
Birth/Neonatal Outcomes ⁴						X													
Mother Efficacy Assessments																			
Opioid Craving Scale		X		X	X		X		X			X			X			X	
Adequacy of Prenatal Care Utilization ⁴						X													
Opioid Overdose Tracking				X	X		X		X			X			X			X	
SOWS-Gossop		X		X	X		X		X			X			X			X	
Other Assessments																			
PROMIS and NMOS		X			X		X		X			X			X			X	
Treatment Services Review		X			X		X		X			X			X			X	
Maternal Research Visit Compensation		\$120		\$40	\$60		\$60		\$60			\$60			\$60			\$70	
Table 3 continued on next page																			

Table 3 continued on next page

CONFIDENTIAL

Table 3: Overview of Assessments and Procedures																				
Perinatal Phase:	Pregnancy					Delivery & Immediate Post-partum	Post-partum													As Needed
	Pre- Screen	Screen/ Base ¹	Random- ization ²	Week 3	Monthly Post-rand ³		Month 1	Month 2	Month 3	Month 4	Month 5	Month 6	Month 7	Month 8	Month 9	Month 10	Month 11	Month 12		
Research Visits		X	X	X	X		X		X			X			X			X*		
Infant Assessments																				
NOWS-related and discharge outcomes ⁴						X														
ASQ-3 ⁹											X							X		
Family Psychosocial Screen ⁹											X							X		
Medical Record Releases ⁺																			X	
Infant assessment compensation											\$30							\$30		
Administrative Forms																				
Locator information form(s) ⁺	X	X			X		X		X			X			X				X	
Study Eligibility			X																	
Study Completion																		X		
Missed Visit and Visit Documentation Form		X	X	X	X		X	X	X	X	X	X	X	X	X	X	X	X		
End of Medication																			X	

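### The primary non-inferiority model leaves out baseline illicit-opioid use, although a screening urine and a 30-day Timeline Followback are already scheduled for every woman

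*Combined protocol and SAP*

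**What the plan says.** Section 10.3.2 fits the share of expected urines that are negative for illicit opioids with a mixed model in which "treatment arm is a fixed effect and the three randomization factors (site, EGA and BUP-SL status at randomization) are random effects". The lower limit of the two-sided 95% confidence interval is compared with -0.15. The postpartum key secondary outcome follows the same approach.

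Other covariates are kept out of this model: "Additional covariates for secondary modeling are described in" section 7.4. There, section 7.4.1 states that "Two covariates will be controlled for in the mother outcomes in addition to study site". The first is "the use of other substances at baseline, which can impact both treatment adherence and illicit opioid use". The second is the route of illicit opioid use, intravenous or not. Neither records whether, or how often, a woman was using illicit opioids at entry.

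Both measures of that are scheduled. Table 3 (section 8.4) marks the urine drug screen and the Timeline Followback in the screening/baseline column. Section 7.6.2 says the Timeline Followback covers "self-reported use of substances for the 30 days before study consent".

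Randomization (section 8.4) balances on site, EGA group and BUP-SL status, not on baseline use. The documents give no reason for leaving baseline use out of the model.

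**The concern.** The baseline value of an outcome is usually among its best predictors. Here a woman's opioid urine result and days of use before entry bear directly on the share of negative urines afterwards. BUP-SL status at randomization is related to both but is only a partial proxy. Inclusion criterion 4 admits women already prescribed buprenorphine and women with moderate or severe OUD who are candidates for it, and a yes/no flag does not show who within each group is still using.

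The plan's own reasoning points the same way. Section 7.4 accepts that such variables can remain an important source of variance after randomization. Section 7.2.1.4 adjusts prenatal care utilization for its own pre-randomization level. The primary outcome gets no such adjustment.

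Two things are at stake: the width of the interval read against -0.15, and the effect on the estimate of a chance difference between arms in baseline use. Both matter more if enrolment ends nearer 176 than 200. Section 10.3.1 calls 176 adequate and reports that the pandemic slowed randomization at every site.

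**Working it through.** **Inputs from the plan.** Margin 0.15 and significance level 2.5%, read from a two-sided 95% interval (sections 10.3 and 10.3.2). Variance 0.11 in each arm, 1:1 allocation, true difference 0 under the alternative, N = 176 or 200, and no variance explained by the strata in the reported case (section 10.4.2).

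**Input that is assumed.** r, the partial correlation between baseline illicit-opioid use and the outcome given site, EGA group and BUP-SL status. The documents give no value. If two baseline terms are fitted, read r² as their joint partial R².

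**Step 1: reproduce Table 8 with no covariate.**

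SE = √(4 × 0.11 / N), and power = Φ(0.15/SE − 1.96).

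- N=176: SE = 0.0500, power = Φ(3.000 − 1.960) = 85.1% (Table 8: 84.9%).
- N=200: SE = 0.0469, power = Φ(3.198 − 1.960) = 89.2% (Table 8: 89.0%).

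The noncentral t gives 84.7% and 88.9%. The plan's figures reproduce.

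**Step 2: adjust for baseline use.**

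Residual variance = 0.11 × (1 − r²). The rest is as in step 1. Equivalent sample size = 176 / (1 − r²).

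| r (assumed) | Residual variance | 95% CI half-width, N=176 | Power, N=176 | Power, N=200 | 176 women are worth |
|---|---|---|---|---|---|
| 0 | 0.1100 | 0.0980 | 85.1% | 89.2% | 176 |
| 0.1 | 0.1089 | 0.0975 | 85.4% | 89.5% | 178 |
| 0.2 | 0.1056 | 0.0960 | 86.5% | 90.4% | 183 |
| 0.3 | 0.1001 | 0.0935 | 88.2% | 91.8% | 193 |
| 0.4 | 0.0924 | 0.0898 | 90.5% | 93.7% | 210 |
| 0.5 | 0.0825 | 0.0849 | 93.4% | 95.8% | 235 |

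The interval shrinks by 1 − √(1 − r²), which is 2.0% at r = 0.2 and 13.4% at r = 0.5.

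**Step 3: what happens if the covariate is useless.** A least-squares simulation with 8,000 runs per cell and r = 0 gave adjusted against unadjusted power of 84.0% and 85.1% at N=176, and 88.3% and 88.2% at N=200. Each figure has a Monte Carlo standard error of about √(0.85 × 0.15 / 8,000) = 0.4 points, so a difference between two separate runs has about 0.6. Neither difference is clear of noise. Type I error was 2.3% to 2.7% across all cells, with and without the covariate.

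**Step 4: chance imbalance.** Assume half the women are baseline-positive and that this is unrelated to the strata. The arm difference in that proportion then has standard deviation √(4 × 0.25 / N), or 0.075 at N=176 and 0.071 at N=200. The probability of a difference above 10 points in either direction is about 18% and 16%. The slope of outcome on baseline status is r × √0.11 / 0.5, or 0.133 at r = 0.2 and 0.332 at r = 0.5. A 10-point imbalance therefore moves the unadjusted estimate by 0.013 to 0.033, which is 9% to 22% of the margin.

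**The case against.** The strongest reply is that nothing in the planned inference is wrong. Adjusting only for the randomization factors is a recognised choice, the comparison is unbiased, the interval already allows for chance imbalance on average, and Table 8 shows more than 80% power. This stands: the point concerns efficiency and robustness, not validity.

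The size of the gain is also uncertain.

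- r is unknown. At r = 0.1 the gain is only about 0.3 points.
- BUP-SL status is already stratified on and modelled, and may carry much of the same information.
- Step 2 starts from the plan's conservative case. If the strata explained 20% of the variance (assumed), the residual would be 0.088 and power at N=176 already 91.8%. Then r = 0.3 would add 2.2 points rather than 3.1, and r = 0.5 would add 5.4 rather than 8.3.
- Section 10.3.2 expects the mixed-model assumptions to fail and names quantile regression as an alternative. The factor (1 − r²) does not carry over to that.
- Missing urines count as positive, so the outcome partly measures attendance, which may weaken its link with baseline use.
- The Timeline Followback ends at consent and screening may take up to 28 days (section 8.3), so it can be somewhat out of date at randomization.
- The target remains about 200, and the plan does not name 176 as a stopping point.

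All of this limits the amount, not the direction. Baseline summaries by arm (section 10.5) and post-hoc work on predictors (section 10.11) could reveal an imbalance, but they would not change the interval that decides non-inferiority. Comfortable stated power is only a partial answer too, since section 10.6 says the power inputs come from limited data. If the variance were 0.15 (assumed), power at N=176 would be Φ(0.15/0.0584 − 1.96) = 73%, and r = 0.4 would bring it back to about 80%.

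**Conclusion.** The concern holds. The primary model and the listed secondary covariates for mother outcomes omit baseline illicit-opioid use, while two measures of it are scheduled at screening/baseline. For an assumed r of 0.2 to 0.5 on the plan's variance of 0.11, adjustment is worth 1 to 8 points of power at N=176 and 1 to 7 at N=200. The gain would be smaller if the strata already explain much of the variance, and close to nothing if r is near zero. The omission is certain; the size of the benefit cannot be settled from the documents. This change should be made, but the trial's validity does not depend on it. The standalone SAP that section 10.4.2 mentions was not available, but section 10.3.2 states the primary model explicitly.

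**What to change.** In section 10.3.2, add baseline illicit-opioid use as fixed effects to both non-inferiority models (pregnancy and postpartum):

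- screening urine positive for any illicit opioid, yes or no, using the same definition as the outcome;
- Timeline Followback days of illicit-opioid use in the 30 days before consent.

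If only one term is wanted, name it and its coding. State the rule for a missing baseline value, for example the overall mean or a missing category. Say that the same terms enter any fallback model, such as quantile regression. Keep the model without baseline use as a sensitivity analysis. If the team prefers not to adjust, the plan should give the reason.

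The cost is a line or two in the protocol and SAP, one or two degrees of freedom, and no new data collection. The change should be fixed before database lock and without reference to outcomes by arm, because in an open-label trial a covariate added later would look data-driven.

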10.4.2 Results

Approach. Given a non-inferiority margin of 0.15, the objective of the sample size simulations was to determine whether there would be sufficient power (i.e., $\geq 80\%$) to detect that margin with a sample size of 200 participants under different assumptions regarding the impact of the three factors used in randomization. There must be sufficient power if the primary analytic model includes the randomization factors as covariates even if they are not associated with outcome. All simulated data assumed 1:1 random allocation between the treatment arms and thus one half in the BUP-XR arm and one half in the BUP-SL arm.

A simulation study was conducted to assess the power. The details of the simulation will be included in the standalone Statistical Analysis Plan. The mean in the BUP-SL arm was assumed to be 0.65 (**section 10.4.1**), and the mean in the BUP-XR arm was assumed to be 0.50 under the null, which corresponds to the specific non-inferiority margin of 0.15, and 0.65 under the alternative. The variance in both arms was fixed at 0.11, with contributions coming from the three random effects capturing randomization strata/factors and additional random error.

Results. The results of the simulations evaluating the power and type I error for the conservative case where all variance is due to random error and none due to the three random effects is given in **Table 8**. Even if the randomization factors are not associated with the outcome, there will still be *at least* 80% power to detect a 0.15 non-inferiority margin with a 2.5% significance level and a sample size of 200. Note that there is at least 80% power with a slightly lower sample size of 176 as well, meaning that the primary outcome is adequately powered with a sample size of 176.

Table 8. Power for a non-inferiority margin of 15% and a significance level of 2.5%.

Proportion of Variance due to Random Error	Mean in BUP-XR Arm	Power (%)	
		N = 176	N = 200
100%	0.50	2.7%	2.4%
	0.65	84.9%	89.0%

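### The primary non-inferiority test is defined and powered on a difference in means, but the plan expects its model to fail and leaves open a quantile-regression fallback with no quantile, trigger, margin or deciding rule

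*Combined protocol and SAP*

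**What the plan says.** All references are to the combined protocol and SAP.

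- **Estimand.** In section 10.3.2 each μ in the hypotheses "is the mean in arm A and Δ the non-inferiority margin".
- **Test.** "To evaluate non-inferiority at the 2.5% significance level, the two-sided 95% confidence interval for the treatment effect" "will be calculated using a mixed effects model where treatment arm is a fixed effect and the three randomization factors" (site, EGA and BUP-SL status) are random effects.
- **Decision rule.** "If the lower limit of the confidence interval is greater than -0.15 (i.e., $\Delta=0.15$), we will reject the null hypothesis".
- **Fallback.** The same paragraph of section 10.3.2 ends by allowing for failure of the mixed model's distributional assumptions, "which is likely, alternative non-parametric methods will be considered for this modelling such as quantile regression".
- **Margin.** Section 10.3.1 takes 15 percentage points from another trial whose outcome is a similar proportion of opioid-free urines, and applies it to both the pregnancy and the postpartum outcome. It mentions no quantile.
- **Power.** In section 10.4.2, "The mean in the BUP-SL arm was assumed to be 0.65" and "the mean in the BUP-XR arm was assumed to be 0.50 under the null", with variance 0.11 in both arms. Table 8 gives power for a mean difference only: 84.9% at N=176 and 89.0% at N=200.
- **Postpartum outcome.** Section 10.3.2 says that it will be analysed in the same way as the primary outcome.

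**The concern.** The fallback is attached to the confirmatory test, and the plan itself calls the condition for using it likely. That expectation is reasonable. The outcome is a proportion between 0 and 1, and missing urines count as positive, so clusters near both ends can be expected. A normal distribution with mean 0.65 and variance 0.11 would put about 15% of women above 1.

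If the analysis then moves to a quantile, it no longer tests the hypotheses as written. The 0.15 margin was set for a mean difference, and Table 8 says nothing about a quantile test. Neither the quantile nor the trigger is fixed, so the choice would be made after outcome data are available, in an open-label trial. Two analysts who both follow the plan could test different quantities and reach opposite conclusions on non-inferiority.

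**Working it through.** **Inputs (sections 10.3.2 and 10.4.2).** Margin 0.15; two-sided 95% CI (one-sided 2.5%); means 0.65 vs 0.65 (alternative) and 0.65 vs 0.50 (null); variance 0.11; 1:1 allocation, n = N/2 per arm; randomization factors without effect, as in Table 8. The documents give no outcome distribution, so the shapes below are assumptions.

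**1. Reproduce Table 8.** SE = √(4 × 0.11/N); power = Φ(0.15/SE − 1.96).
- N=176: SE = 0.0500; Φ(3.000 − 1.96) = 85.1% (plan: 84.9%).
- N=200: SE = 0.0469; Φ(3.198 − 1.96) = 89.2% (plan: 89.0%).

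**2. Does the margin carry over?** A beta distribution with mean m and variance 0.11 has a + b = m(1 − m)/0.11 − 1.
- m = 0.65: a + b = 0.2275/0.11 − 1 = 1.068, giving Beta(0.694, 0.374), which is U-shaped with median 0.757.
- m = 0.50: a + b = 0.25/0.11 − 1 = 1.273, giving Beta(0.636, 0.636), median 0.500.

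A mean deficit of 0.150 is then a median deficit of 0.757 − 0.500 = 0.257.

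**3. Power of a median test against 0.15, true difference zero.** SE = 1/(f√(2n)), where f is the density at the median; power = Φ(0.15/SE − 1.96).

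| Assumed shape (variance 0.11) | f | SE, N=176 / 200 | Power, N=176 / 200 |
|---|---|---|---|
| Beta, mean 0.65 | 0.820 | 0.0919 / 0.0862 | 37.2% / 41.3% |
| Beta, median 0.65 | 0.766 | 0.0984 / 0.0923 | 33.2% / 36.9% |
| Normal | 1.203 | 0.0627 / 0.0588 | 66.8% / 72.3% |

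The second row is included because section 10.4.1 takes the 0.65 from a median in the cited study.

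Simulation with a percentile-bootstrap interval (4,000 trials) agrees: 38.2% and 41.7% for the first row, 66.5% and 72.0% for the normal. Beta-binomial urine counts (8–32 samples per woman, total variance 0.11) gave 39.8% and 44.4%.

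The interval method matters too. With the kernel-based standard error usual in quantile regression, the first row gave 53.3% and 57.9% (1,500 trials).

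**4. Other quantiles.** For the first-row beta at N=176, power is about 25% at the 25th percentile, 37% at the 50th, 63% at the 60th and about 100% at the 75th. The unstated quantile alone can settle the result.

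**5. Does non-normality require leaving the mean?** On the beta data, the ordinary unequal-variance interval for the mean difference had 84.6% power (N=176) and 89.4% (N=200). At a true deficit of 0.15 (0.65 vs 0.50) it declared non-inferiority in 2.2% of 1,500 trials. Separate runs gave 1.6% to 3.1%, around the nominal 2.5%. At these sample sizes the mean comparison works without normal data.

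**The case against.** **The text commits to nothing.** Alternatives are only to be considered, and quantile regression is one example. A reader might infer that the plan will switch to a median test. The documents do not say that, and no quantile is named. The phrase about this modelling also follows a sentence on secondary models, so its scope is not beyond doubt. But the condition refers to the mixed effects model, which that paragraph introduces for the primary interval, so the primary reading is the natural one. What stands is that the fallback is open, not that a switch is certain.

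**No single power figure can be charged to the plan.** A reader might infer that the fallback has about 38% power. That figure needs a beta shape, the median, N=176, no true difference and a bootstrap interval. Section 10.4.2 leaves the simulation details to a standalone SAP that is not among these documents. Only the range, labelled as illustrative, can be supported.

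**A reader might infer that the fallback would pass an inferior treatment too often.** The plan's inputs do not show this. With beta outcomes and means of 0.65 vs 0.50, the bootstrap median test declared non-inferiority in about 0.1% of trials. Inflation appears in a hypothetical population with 70% vs 56% of women all-negative and means of 0.75 vs 0.60. That population has variances of at least 0.146 and 0.204, against the plan's 0.11 in both arms. It shows that the two estimands can diverge in either direction, not an error rate for this trial.

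**A standalone SAP may settle the matter.** It may, but section 10.4.2 refers to it only for the simulation details.

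**Conclusion.** The point holds as a defect in the specification of the confirmatory test. The hypotheses, margin and power all concern a mean difference. The plan expects the model for that difference to fail its assumptions, and names a possible replacement that targets another quantity, with no quantile, trigger, margin or deciding rule. The postpartum non-inferiority outcome inherits the problem.

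None of this depends on a distributional assumption; only the size does. With variance 0.11, no true difference, the median and the 0.15 margin, large-sample power is about 33–42% for beta outcomes and 67–72% for a normal outcome across N=176–200. The beta-binomial and kernel-interval variants fall between these ranges. All are below 80% and below Table 8. The mean comparison keeps its stated power and close to its nominal error on the same non-normal data, so the fallback solves no problem that the primary test has at this sample size.

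**What to change.** State in section 10.3.2, for both the pregnancy and the postpartum outcome:

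1. The adjusted difference in means, compared with −0.15, is the deciding analysis whatever the outcome distribution.
2. If residuals are clearly non-normal, the 95% CI comes from heteroscedasticity-robust standard errors, or from a bootstrap that resamples within treatment arm only.
3. Quantile regression, with its quantile named in advance, is a sensitivity analysis and does not decide non-inferiority.

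The bootstrap should not resample within every site × EGA × BUP-SL cell. With about 10 sites there are 10 × 2 × 2 = 40 cells, or 88/40 = 2.2 to 100/40 = 2.5 women per arm per cell. If cells are equally likely, 88 women occupy about 40 × (1 − 0.975^88) = 35.7 cells. Resampling within them shrinks the variance by about (88 − 35.7)/88 = 0.59 and the standard error by about 0.77. The one-sided error rises to about Φ(−1.96 × 0.77) = 6.5%. Simulation of the unadjusted difference, assuming no stratum effects, gave 7.3% at N=176 and 6.8% at N=200, against 2.7% and 3.1% for the ordinary interval.

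The cost is two or three sentences. No new data are needed, and Table 8 remains the relevant power statement.
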